#### *Exclusion criteria*

- Novices with > 5 hours experience of any robotic system.

### Outcomes:

#### *Primary outcome measures:*

- time-based score for each task

#### *Secondary outcome measures:*

- modified Global evaluative assessment of robotic skills score for each task
- the training time to reach the mastery learning level for the novice group and cardiac surgery novices; both total time and for each task.

### Statistical plan and data analysis

Within the current literature exists the only study assessing robotic cardiac surgery simulation training with sample size of 10 participants in the wet lab group. The reports on growth models and learning curve dataset recommend least 3 repeated observations per individual. We plan to recruit 16 participants in the novice and 5 robotic cardiac surgeons from different international sites in the experienced group. We plan to include equal numbers of cardiac (8) and non-cardiac trainees (8). Additionally, two surgeons with experience in robotic cardiac surgery from two different sites will be recruited to rate all the training sessions.

Based on the previous study we hypothesize that the subjects in the novice group will be able to achieve the mastery learning within 5 trainings sessions and thus fulfil the requirement of at least 3 repeated observations.

STATA will be used for statistical analysis. The Kruskal-Wallis test will be used to examine a difference between the novice and the expert group at base-line. We will use the Mann-Whitney U test to compare continuous variables. A two-sided significance level of 0.05 will be used. The internal consistency will be evaluated by Cronbach's alpha, and the test/retest reliability of the last two training sessions using intra-class correlation coefficient.

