All tasks will be recorded on the robot's camera and evaluated blinded using the modified Global Evaluative Assessment of Robotic Skills (mGEARS) score (Appendix 1) by two not participating surgeons with experience in robotic cardiac surgery from two different sites in Europe and North America. In modified GEARS score the tasks will not be rated on autonomy domain as autonomy cannot be evaluated from recordings.

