### 4. Internal structure:

To examine the reliability of the final simulator task, the internal consistency and test/retest reliability will be assessed. The internal consistency of TBS and mGEARS scores will be used for the assessment of trainee performance for the base-line task. The test/retest reliability will be calculated by comparing the trainees' TBS and mGEARS performance in the last 2 training sessions.

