## 5. Consequences:

To investigate the consequence of testing we will define a pass/fail level to be used for mastery learning. The pass/fail level will be determined using the “contrasting groups method” for the mean TBS and mGEARS score for the last two attempts in the experienced group.

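### Agreement between the two mGEARS raters is not analysed, so the planned reliability statistics can look good while the raters stably disagree

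*Combined protocol and SAP*

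**What the plan says.** All references are to the combined protocol and SAP.

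- **Rating.** Under 2. Response process: "All tasks will be recorded on the robot's camera and evaluated blinded using the modified Global Evaluative Assessment of Robotic Skills (mGEARS) score", and the scoring is done "by two not participating surgeons with experience in robotic cardiac surgery from two different sites in Europe and North America". The Statistical plan and data analysis section confirms that "two surgeons with experience in robotic cardiac surgery from two different sites will be recruited to rate all the training sessions".
- **Reliability.** Under 4. Internal structure, "the internal consistency and test/retest reliability will be assessed". Internal consistency concerns TBS and mGEARS at base-line. Test/retest reliability comes from "comparing the trainees' TBS and mGEARS performance in the last 2 training sessions".
- **Statistics.** The Statistical plan states: "The internal consistency will be evaluated by Cronbach's alpha, and the test/retest reliability of the last two training sessions using intra-class correlation coefficient".
- **Use of the score.** mGEARS is a secondary outcome. It enters the base-line comparison of experts and novices (3. Relations to other variables) and the pass/fail level, which is set "for the mean TBS and mGEARS score for the last two attempts in the experienced group" (5. Consequences).

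No section plans an inter-rater ICC, kappa, limits of agreement or generalizability analysis. None describes rater calibration or says how the two raters' scores are combined.

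**The concern.** mGEARS is a judgement on five domains, each scored 1 to 5 against verbal anchors. Two surgeons from different continents may read those anchors differently, so disagreement between them is a likely source of error.

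If alpha is taken over the domains, a rater's overall impression of a trainee (halo) raises all five domain scores together, and alpha counts it as true score. The test/retest ICC compares sessions. A leniency gap that is the same in both sessions cancels, and a rater's stable view of a particular trainee is counted as trainee variance.

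The primary objective is validity evidence, and internal structure is one of its five sources. The study could follow its plan, report two favourable coefficients and recommend an mGEARS cut-off whose meaning depends on who rates.

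**Working it through.** The documents state no expected alpha, ICC or variance component, so there is no planned figure to reproduce. Everything below illustrates the mechanism under assumed variances.

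**Inputs from the documents:** 2 raters per recording; 5 domains scored 1 to 5 (total 5 to 25); 16 novices + 5 experts = 21 participants.

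**Step 1. Closed form.** Assume subject variance vs = 1, domain residual ve = 0.5 (so ve/5 = 0.1) and rater-specific halo variance vr. Assume alpha is taken over the five domains of one rater.

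- Alpha = (vs + vr) / (vs + vr + ve/5)
- Single-rater reliability = vs / (vs + vr + ve/5)
- Reliability of the two-rater mean = vs / (vs + (vr + ve/5)/2)

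| vr | Alpha | Single rater | Mean of two |
|---|---|---|---|
| 0.25 | 1.25/1.35 = 0.93 | 1/1.35 = 0.74 | 1/1.175 = 0.85 |
| 0.5 | 1.5/1.6 = 0.94 | 1/1.6 = 0.63 | 1/1.3 = 0.77 |
| 1.0 | 2/2.1 = 0.95 | 1/2.1 = 0.48 | 1/1.55 = 0.65 |

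With no halo, alpha is already 1/1.1 = 0.91, so its rise is small. What matters is that alpha does not fall as the raters diverge. Computing alpha on the two-rater mean does not help: at vr = 1.0 it is 1.5/1.55 = 0.97, against a reliability of 0.65.

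**Step 2. Does the test/retest ICC catch it?** Step 1 has no sessions and no leniency term, so this was simulated: 16 trainees, 2 crossed raters, 2 sessions, 5 items rounded to 1–5, 2000 runs per scenario. Test/retest used the mean of the two raters, which is also an assumption. Medians:

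| Scenario (assumed variances) | Alpha, single rater | Test/retest ICC | Inter-rater ICC, absolute agreement |
|---|---|---|---|
| Raters agree (trainee 0.8) | 0.95 | 0.91 | 0.91 |
| One rater 1 point per domain more lenient (trainee 0.8) | 0.95 | 0.91 | 0.57 |
| One rater 1.5 points more lenient (trainee 0.8) | 0.94 | 0.90 | 0.38 |
| Stable rater-by-trainee 0.6, trainee 0.4 | 0.95 | 0.89 | 0.40 |
| Session-varying rater error 0.4, trainee 0.4 | 0.94 | 0.60 | 0.49 |
| Session-varying rater error 0.8, trainee 0.4 | 0.96 | 0.46 | 0.33 |
| Narrow trainee range 0.1, raters agree | 0.79 | 0.57 | 0.63 |

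Stable disagreement (rows 2 to 4) leaves both planned statistics high. Session-varying error (rows 5 and 6) lowers test/retest, though it cannot be separated there from real change in the trainee.

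**Step 3. Effect on a cut-off.** A leniency gap of 1 point per domain is 5 × 1 = 5 points on the total before rounding and truncation (mean absolute rater difference 4.8 in the simulation). A cut-off set on the two-rater mean would then lie about 2.5 points from each rater's own scale.

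**Step 4. Precision of the missing analysis.** For two raters, F = (1 + ICC)/(1 − ICC); at ICC = 0.8, F = 9. The exact F-based 95% CI, computed for the consistency form, is 0.57 to 0.91 with 21 participants and 0.52 to 0.93 with the 16 novices. At ICC = 0.6 with 21 participants it is 0.24 to 0.82.

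**The case against.** **The plan does not ignore rater error altogether.** A reader might infer that it does. Rows 5 and 6 of Step 2 show otherwise: session-varying rater error reduces the planned test/retest ICC. This stands and limits the point to stable disagreement.

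**The items for alpha are not defined.** TBS is one number per task and has no domains, so its alpha needs other items, perhaps the three tasks. The same could be meant for mGEARS, or raters could be the items, in which case alpha would reflect rater consistency. This stands as a caveat on Step 1. It does not remove the point: a halo that is stable across tasks would still inflate alpha, and alpha over raters would still miss leniency.

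**Good coefficients are not assured.** The last two sessions are near mastery, and a narrow range of trainees can pull test/retest down even when raters agree (0.57 in the last row). The claim is only that the coefficients can look good.

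**The consequences are limited.** A reader might infer that rater leniency could create the base-line difference between experts and novices. Both raters score every recording, blinded, so leniency shifts both groups alike and cannot by itself produce it. Nor is the primary outcome affected: TBS is not an mGEARS rating, and TBS sets the training mastery level and tracks the later rounds. It would also be wrong to call the ratings unused; they feed the comparison, the reliability analyses and the pass/fail level. These limits stand.

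**Conclusion.** The concern holds in a limited form. Agreement between the two mGEARS raters, and the rule for combining their scores, are not prespecified. The two planned reliability statistics can be high while the raters stably disagree. For example, alpha of 0.95 and test/retest of 0.91 can coexist with an inter-rater ICC of 0.57 when one rater is 1 point per domain more lenient.

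The sizes rest entirely on assumed variances and, in Step 1, on alpha being taken over the five domains. They show what could go unseen, not what will happen. The omission weakens the mGEARS internal-structure evidence and leaves it unknown whether the mGEARS pass/fail level would carry over to other raters. The documents do not support extending this to TBS, the mastery criterion based on it, or the direction of the expert/novice comparison. It should be corrected before analysis, since the data will already exist and the gap bears on the primary validity objective.

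**What to change.** In 4. Internal structure and in the Statistical plan and data analysis, add:

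- Inter-rater reliability of the mGEARS total, per task, by a two-way random-effects absolute-agreement ICC, for a single rater and for the mean of two, with 95% CI.
- At base-line, report it for novices alone and for all participants. Pooling experts with novices widens the range and tends to raise the ICC, so both are needed.
- Report the same ICC, with the mean difference between raters, for the attempts used to set the pass/fail level. A narrow range among experts can make the ICC unstable there, and the mean difference shows leniency directly.
- Use the two-rater mean in all mGEARS comparisons and in the pass/fail level.
- State the items over which alpha is computed. Report the inter-rater ICC alongside alpha and test/retest, not in place of them, because they measure different properties.

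The cost is one extra analysis of ratings already planned, with no added participants or scoring. The intervals will be wide (Step 4), so the result should be read with its interval and not against a single threshold.

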## **Objectives**

*Primary:*

- to investigate validity evidence for simulation-based assessment using the wet lab robotic cardiac surgery model.

*Secondary:*

- to analyze performance curves in the wet lab for a robotic cardiac surgery model.
- to assess rate of skills acquisition of cardiac robotic skills in cardiac surgery trainees versus non-cardiac surgery trainees.

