## **Materials and methods**

We aim to assess the validity evidence for the wet lab robotic cardiac surgery simulation model using the contemporary framework for validity proposed by Messick, which includes five sources of validity evidence: content evidence, response process, relations to other variables, internal structure, and consequences.

We will test the validity evidence for the three wet lab tasks used in robotic cardiac surgery using three groups of participants: experienced robotic cardiac surgeons (5), robotic cardiac surgery novices (8) and robotic non-cardiac surgery novices (8).

Wet lab simulator: tasks will be performed in porcine models with the da Vinci Xi Surgical System (Intuitive Surgical, California, USA).

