### 3. Relations to other variables:

We will analyze variation in performance scores (TBS and mGEARS) between experienced robotic cardiac surgeons and robotic novices during their base-line performance. We will use TBS score for the assessment of novice performance during the subsequent training rounds.

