### Selection of participants:

#### *Inclusion criteria*

- Experienced robotic cardiac surgeons: robotic surgeons with total volume > 50 robotic cardiac operations and at least 20 robotic cases annually.
- Cardiac surgery novices: on-going or completed cardio-thoracic residency.
- Non-cardiac surgery novices: on-going or completed surgical specialty residency (gynecology, urology, general surgery, ENT surgery).

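### Does loose use of the word novice, with Mann-Whitney tied to no comparison, leave the base-line analysis undefined?

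*Combined protocol and SAP*

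**What the plan says.** All references are to the combined protocol and SAP.

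- **Statistical plan and data analysis**, group sizes: "We plan to recruit 16 participants in the novice and 5 robotic cardiac surgeons from different international sites in the experienced group". The next sentence divides the 16 equally into cardiac and non-cardiac trainees.
- **Same section**, tests: "The Kruskal-Wallis test will be used to examine a difference between the novice and the expert group at base-line", followed by "We will use the Mann-Whitney U test to compare continuous variables". The level is two-sided 0.05.
- **3. Relations to other variables**: performance on the time-based score (TBS) and mGEARS is compared "between experienced robotic cardiac surgeons and robotic novices during their base-line performance".
- **Materials and methods**: three groups of 5, 8 and 8.
- **Secondary outcome measures**: "the training time to reach the mastery learning level for the novice group and cardiac surgery novices".
- **Objectives**, secondary: "to assess rate of skills acquisition of cardiac robotic skills in cardiac surgery trainees versus non-cardiac surgery trainees".
- **Inclusion criteria**: the experts are "robotic surgeons with total volume > 50 robotic cardiac operations and at least 20 robotic cases annually".

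**The concern.** Three features of the text pull against each other.

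1. The statistical plan uses the novice group for all 16 novices. The secondary outcome sets the same term beside the cardiac novices, which suggests the 8 non-cardiac novices.
2. Kruskal-Wallis is normally chosen for three or more groups, and the design has three, yet the sentence names two.
3. Mann-Whitney has no groups, outcome or time point attached.

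The base-line comparison supplies the relations-to-other-variables evidence for the primary objective. If two analysts could run different tests from the same text, they could reach different answers with only 21 people. There is also a point of interpretation: every expert is a cardiac surgeon and half the novices are not, so a pooled contrast mixes robotic experience with cardiac background.

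**Working it through.** **Counts.** 5 + 16 = 21 and 5 + 8 + 8 = 21, so the two descriptions cover the same people. The plan states no power, effect size or SD, so there is no sample-size figure to reproduce.

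**Is the named test valid for 5 v 16?** Take n1 = 5, n2 = 16, N = 21, and let R be the experts' mean rank. The overall mean rank is 22/2 = 11.

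- Mann-Whitney: U has mean 5 × 16/2 = 40 and variance 5 × 16 × 22/12 = 146.67. Since U − 40 = 5(R − 11), Z² = 25(R − 11)²/146.67 = 0.1705(R − 11)².
- Kruskal-Wallis: H = 12/(21 × 22) × [5(R − 11)² + 16(R₂ − 11)²]. The deviations satisfy 5(R − 11) = −16(R₂ − 11), so H = (12/462) × 5 × (21/16) × (R − 11)² = 0.1705(R − 11)².

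Thus H = Z². Referring H to chi-square on 1 df gives the same p-value as the two-sided normal test without continuity correction. Over 2,000 simulated 5 v 16 data sets the largest difference in p was 3 × 10⁻¹⁴. Choosing between the two test names makes no difference here, unless the exact version is used (about 4 points less power at 1.0 and 1.5 SD).

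**Which groups does the text give?**

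| Question | Text that answers it | Result |
|---|---|---|
| Base-line comparison | Relations to other variables; the test sentence itself | experts v novices |
| Size of the novice group in that section | Recruitment sentence of the statistical plan | 16 |
| Training-time contrast | Secondary objective, with the equal split | 8 v 8 |
| Test for training time | Two groups, continuous variable | Mann-Whitney |

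**What would the other reading cost?** Simulation used normal scores, equal SD, 40,000 trials per scenario and one task. Both novice groups lie the same assumed distance below the experts.

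| Expert lead (SD) | 5 v 16 | 5/8/8 | Difference (points) |
|---|---|---|---|
| 0 | 5.0% | 4.5% | – |
| 1.0 | 43% | 29% | 14 |
| 1.5 | 76% | 60% | 16 |
| 2.0 | 94% | 85% | 9 |
| 2.5 | 99% | 96% | 3 |

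A separate run of 4,000 trials per scenario gave 42% v 29%, 76% v 60% and 95% v 85% at 1.0, 1.5 and 2.0 SD. Type I error is held under both readings.

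**Cardiac background.** Suppose the experts only equal the cardiac novices, and both lie 0.5, 1.0 or 1.5 SD above the non-cardiac novices. The 5 v 16 test then rejects in 7, 12 and 18% of trials, and the three-group test in 12, 39 and 75%. The reading that the text supports is much the less sensitive to background alone.

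**The case for a change.** The best case for a change is that one sentence would remove the doubt at no cost, and that the choice should be settled before data are seen. With 21 people the choice of reading can move power by 16 points. A three-group rejection could also be reported as expert-novice discrimination when only cardiac background differs.

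Some of this stands. Mann-Whitney is indeed unassigned, and the term in the secondary outcome is loose. It most likely means the non-cardiac novices, though it could also mean results for all novices and then for the cardiac subset. Neither meaning creates a wrong test: that line names no test, and nothing in the plan tests all 16 against 8 of themselves.

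The rest is weaker. The three-group reading has to set aside the two places that describe the base-line comparison. The background scenario requires surgeons with more than 50 robotic cardiac operations to do no better than novices with at most 5 hours on any robot. Even then the experts truly differ from the pooled novices, so a rejection is not a false positive for the comparison stated. An estimate for experts against the 8 cardiac novices would be a reasonable addition to a report. An unassigned Mann-Whitney test does not exclude it, and leaving it unspecified breaks no rule in the plan.

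**Conclusion.** No change follows. The text points to 5 v 16 at base-line, where the named test is valid, and to 8 v 8 for training time, where Mann-Whitney is the obvious choice. What remains is missing detail that an analyst fills sensibly, and one loosely used term.

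The three-group reading would cost 14 to 16 points of power at an expert lead of 1.0 to 1.5 SD and 3 points at 2.5 SD, with type I error held either way. These figures rest on assumed shifts and on normal scores with equal SD. They ignore ties, although a major error sets the TBS to zero and could produce some. They show the order of size only. The identity of the two tests on two groups depends on none of these assumptions, and it survives ties when both tests use the usual correction. The mixing of robotic experience with cardiac background limits how the pooled contrast is interpreted, but it does not invalidate the test.

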### 2. Response process:

All participants will receive a short oral introduction to the da Vinci Xi Surgical System and will be shown videos of robotically assisted cardiac procedures highlighting basic operative techniques and relevant anatomy. They will then complete the three previously selected tasks to familiarize themselves with the wet lab simulator. Finally, they will complete all 3 tasks again and this will be used to assess their base-line performance.

Next, five experienced robotic cardiac surgeons from different international sites will perform each task 4 times more. Subjects in the cardiac and non-cardiac groups will perform the tasks until mastery is achieved based on the performance of the expert robotic surgeons. To ensure

the successful completion of the task, each participant will be required to pass each exercise 2 consecutive times with the only one failure between the attempts allowed.

The mastery learning level for the tasks will be calculated from the mean time-based score (TBS) of the experienced surgeons 2 last attempts for each task.

Time-based scoring equation will be calculated as follows (adapted from Valdis et al):

$$\text{Score} = \text{Max time} - \text{Completion time} - \text{Errors}$$

-Max time is the total time that an individual will be allowed to complete the task during the base-line performance.

-Completion time is either;

- 1) The mean time for completion of each expert's last 2 attempts which will be used to calculate the mastery learning level based on the formula above
- 2) The time taken by each study participant to complete the task

- Errors will be divided in minor and major ones. A minor error will result in adding a 10 second penalty time to the TBS equation. A major error will result in a score of zero, regardless of time to completion.

Minor errors:

- 1) moving robotic arms out of view
- 2) robotic arm collision
- 3) drop of the needle

Major errors:

- 1) avulsion of ITA or suturing model
- 2) tearing/ fraying the suture
- 3) gross tissue damage (specifically with the cautery)

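### The base-line expert-novice comparison is planned only as a significance test, with no estimate of how well the score separates the groups

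*Combined protocol and SAP*

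**What the plan says.** The primary objective is validity evidence for the wet lab assessment, and TBS for each task is the primary outcome. The section on relations to other variables compares TBS and mGEARS "between experienced robotic cardiac surgeons and robotic novices during their base-line performance". For later rounds it says: "We will use TBS score for the assessment of novice performance during the subsequent training rounds".

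The statistical section names the test: "The Kruskal-Wallis test will be used to examine a difference between the novice and the expert group at base-line". It adds: "A two-sided significance level of 0.05 will be used". On numbers it says: "We plan to recruit 16 participants in the novice and 5 robotic cardiac surgeons from different international sites in the experienced group". The novices are split equally, 8 cardiac and 8 non-cardiac. A Mann-Whitney test is listed for continuous variables, but not tied to any comparison.

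The other planned analyses are Cronbach's alpha, a test/retest intra-class correlation and a contrasting-groups pass/fail level. None of them is described as giving an estimate of expert-novice separation. The plan does not say whether the Kruskal-Wallis test is run on two groups, as its wording suggests, or on the three groups defined under Materials and methods.

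**The concern.** The score is meant to carry a pass mark that decides when a trainee may go on to patients. What matters for that use is how far expert and novice scores overlap. A p value below 0.05 shows only that the overlap is less than chance alone would readily produce. It does not give the size of the overlap or how precisely it is known.

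With five experts the two questions can have quite different answers. As written, a result just under 0.05 could be reported as validity evidence for a score that puts about a fifth of expert-novice pairs in the wrong order, and the planned analysis would not show this.

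**Working it through.** **Inputs.** From the statistical section: 5 experts, 16 novices (8 + 8), two-sided 0.05. Assumed: no ties. The plan states no power, effect size or separation target, so there is no figure to reproduce.

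**Step 1. Pairs.** 5 × 16 = 80. Let U be the number of pairs in which the novice outscores the expert. Then AUC = 1 − U/80.

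**Step 2. Two-group test.** Without ties, the Kruskal-Wallis statistic on two groups is z², where z = (40 − U)/√(5 × 16 × 22/12) = (40 − U)/12.11. It is referred to chi-square on 1 df.

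| U | Misordered | AUC | Kruskal-Wallis p (chi-square) | Exact Mann-Whitney p |
|---|---|---|---|---|
| 15 | 18.75% | 0.8125 | 0.0390 | 0.0401 |
| 16 | 20.0% | 0.80 | 0.0475 | 0.05003 |
| 17 | 21.25% | 0.7875 | 0.0575 | 0.0616 |

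The limit is 16 of 80 with the chi-square p value and 15 of 80 with the exact one. An example with U = 16: four experts take the top four places and the fifth scores below all 16 novices.

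**Step 3. Precision at the limit.** Hanley-McNeil standard error at A = 0.80:
- Q1 = A/(2 − A) = 0.6667; Q2 = 2A²/(1 + A) = 0.7111; A² = 0.64.
- Variance = [0.16 + 4 × (0.6667 − 0.64) + 15 × (0.7111 − 0.64)]/80 = 1.333/80 = 0.01667.
- SE = 0.129. At A = 0.8125 it is 0.126.

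The 95% interval at A = 0.80 is 0.80 ± 1.96 × 0.129, about 0.55 to 1.00 after cutting the upper limit at 1. On the logit scale it is about 0.45 to 0.95.

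**Step 4. Three-group test (5/8/8, 2 df, critical value 5.99).**
- If the two novice groups have equal mean ranks, H again equals z². Significance needs z > 2.448, so U ≤ 40 − 2.448 × 12.11 = 10.4. The limit is then 10 of 80 (12.5%).
- If the novice groups differ, the test can reject with no expert-novice separation. Example: experts at ranks 2, 5, 14, 17, 18 (sum 56); one novice group at 1, 3, 4, 6, 7, 8, 12, 15 (sum 56); the other at 9, 10, 11, 13, 16, 19, 20, 21 (sum 119). H = 12/(21 × 22) × (56²/5 + 56²/8 + 119²/8) − 66 = 6.45, which is significant. The experts win 56 − 15 = 41 of 80 pairs, so 39 are misordered and the AUC is 0.51.

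**The case against.** **The limit is an edge case.** A score that discriminates strongly would misorder far fewer pairs and give a much smaller p value. That is true. The figure shows what p < 0.05 allows, not what to expect. It also depends on two groups, a chi-square p value and no ties. Ties are likely, since every major error sets TBS to zero, and they would move the limit.

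**A p value is never an effect size, and nothing forbids reporting one.** This is fair, and it is why the point is an improvement rather than a fault that undermines the study. But the comparison serves the primary objective, and the plan should name its main result in advance.

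**A reader might infer more:** that the base-line gap only reflects novices meeting the console for the first time, so discrimination should be claimed only if the gap persists at a later attempt. The exclusion of "Novices with > 5 hours experience of any robotic system" and the plan that "five experienced robotic cardiac surgeons from different international sites will perform each task 4 times more" make this tempting. The documents do not support it, for three reasons:
- Base-line comes after an introduction, videos and a complete familiarisation round of all three tasks, and novices may have up to 5 hours of earlier robotic experience. Some remaining unfamiliarity cannot be excluded, but base-line is not first contact.
- Later novice attempts are already judged against a mastery level taken from the experts' last two attempts, and training time to that level is a secondary outcome. A gap that closed quickly would show up there.
- Novices train until they match the experts, so a shrinking gap is the intended effect. Familiarity and skill both improve with practice, so a later comparison cannot separate them. If learning had left a true gap of 1 SD (an assumption; normal scores, exact test, 5 v 16), simulated power is about 39%. A persistence rule would then withhold the claim from a working score in about 61% of trials.

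**Conclusion.** The point holds in a limited form. The only test the plan names for expert against novice scores is a base-line significance test, with no measure of separation. On two groups without ties it is significant with up to 16 of 80 pairs misordered, or 15 of 80 with exact p values. The AUC is then about 0.80 with a standard error of about 0.13. On three groups with equal novice mean ranks the limit falls to 10 of 80, but a rejection then need not concern the experts at all.

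This does not show that the score discriminates poorly or that the base-line gap is spurious. It shows that the planned analysis would not tell a reader how good the discrimination is.

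**What to change.** In the statistical section, for each task and for both TBS and mGEARS:

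1. Make the main base-line validity result the probability that an expert outscores a novice. This is the AUC: correctly ordered pairs out of 80, with ties counted as half, including pairs in which both have a TBS of zero after a major error.
2. Report it with a 95% confidence interval and name the interval method in advance. The two intervals in step 3 differ visibly. At perfect separation (AUC = 1) the Hanley-McNeil standard error is zero, so a method that copes with that case, such as a score-type interval, is preferable.
3. State that the supporting p value comes from the two-group comparison, 5 v 16. Report any comparison between the novice groups separately.
4. Base the discrimination claim on the AUC and its interval, not on p < 0.05.

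If wanted, show the AUC at later attempts descriptively, with the number of novices contributing, and place no condition on the claim.

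The cost is analysis wording only; no extra data or participants are needed. With five experts the intervals may be wide, which is the study's real precision.
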